4.2.2. Vital Signs, Physical Examination, Height, and Weight

Baseline vital signs (systolic blood pressure, diastolic blood pressure, respiratory rate, and heart rate (pulse rate), physical examination, height, and weight are performed only at Screening. Given the screening and baseline visits can be combined, baseline vital signs, physical examination, height, and weight are those assessments performed during the Screening visit.

4.2.3. Inhalational Flow Values

The baseline inspiratory flow values are computed using the set of inhalations taken by the patient during study day 1 through day 7. Among these inhalations, the inhalation with the highest MIF value is considered the ‘baseline inhalation’. The baseline MIF, inhalational volume, inhalation duration, and time to MIF values are those of the identified ‘baseline inhalation’. If no inhalations were taken during study day 1 through study day 7, the ‘baseline inhalation’ is the first available inhalation after study day 7.

4.2.4. Total Daily Steps

Baseline TDS is the average number of daily steps a patient completes, computed using the daily steps recorded during the first 7 days of study participation (study day 1 through study day 7). The average will be calculated as the sum of the daily TDS divided by the number of days with nonmissing TDS. If no step data are available for study day 1 through study day 7, the ‘baseline TDS’ is the first available TDS after study day 7.

Baseline TDS are computed for those patients in the ankle accelerometry analysis set.

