APPENDIX B. STUDY PROCEDURES AND ASSESSMENTS BY VISIT

1. Procedures During Screening Visit (Visit 1, Day -14 to Day 1)

The screening visit (visit 1) will take place not more than 2 weeks before the baseline visit (visit 2) and may occur at the same time as the baseline visit (visit 2). The following procedures will be performed at visit 1:

- obtain written informed consent before any study-related procedures are performed
- review inclusion and exclusion criteria
- assign patient number
- obtain medical history
- obtain prior medication and treatment history
- physical examination, including height and weight
- vital signs measurements, including blood pressure, respiratory rate, and heart rate
- urine pregnancy test for women of childbearing potential
- inform patients of study compliance for multidose dry powder inhaler with an eModule (eMDPI) and accelerometer and requirement for provider visit in the event of a clinical exacerbation of COPD (CE-COPD)
- assess for COPD exacerbations
- prior and concomitant medication inquiry

2. Procedures During Intervention Period

a. Baseline Visit (Visit 2, Day 1)

Patients who meet the inclusion and exclusion criteria at visit 1 may continue to visit 2, when baseline assessments will be conducted (visits 1 and 2 may be combined).

The following procedures will be performed at visit 2:

- review inclusion and exclusion criteria
- inform patients of study compliance for eMDPI and accelerometer and requirement for provider visit in the event of a CE-COPD
- assess for COPD exacerbations
- inquire about adverse events
- train on use of wearable accelerometers and dispense to the subset of patients who consent to using the devices
- train on the use, collection, and accountability of inhaler and dispense albuterol sulfate (ABS) eMDPI
- concomitant medication inquiry

b. Phone Visits (Visits 3 and 4, Days 28 and 56±7 days, respectively)

Patients will be contacted by phone and do not need to visit the investigational center.

The following information will be discussed during the phone call:

- assess for COPD exacerbations and treatments (Investigational centers must obtain source documentation for all COPD exacerbations to confirm the accuracy of the information obtained from the patient.)
- inquire about adverse events
- concomitant medication inquiry
- inform patients of study compliance for eMDPI and accelerometer and requirement for provider visit in the event of COPD

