^a Investigational centers must obtain source documentation for all COPD exacerbations that occur during the treatment period to confirm the accuracy of the information obtained from the patient.

^b Height will be measured at the screening visit only.

^c Vital signs measurements will include blood pressure, respiratory rate, and heart rate.

^d Wearable accelerometers for a subset of patients who agree to participate at specific investigational centers will be dispensed at visit 2, and SDI and TDS data will be collected continuously from visit 2 through visit 5 via the wearable accelerometer. Instructions for proper use of the devices will be provided to patients at visit 2. The devices will be collected at visit 5.

^c Patients will receive initial eMDPI devices at visit 2 based on anticipated usage pattern. In the event that additional eMDPI devices are needed, patients will be required to visit the investigational center to receive them. Patients will be instructed to return all inhalers to the investigational center at the last study visit or earlier, including at the early termination visit, as well as at any other point if there is a problem with the inhaler. Instructions for dispensing, proper clinical use, and collecting ABS eMDPI will be provided to patients at visit 2 and reviewed during the monthly calls.

ABS = albuterol sulfate; CE-COPD = clinical exacerbation of chronic obstructive pulmonary disease; COPD= chronic obstructive pulmonary disease; eMDPI=multidose dry powder inhaler with an eModule; SDI = sleep disruption index; TDS=total daily step; V = visit.

Note: Screening and baseline visits may be combined.

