4.2. Specification of Baseline Values

4.2.1. Albuterol Use

Baseline albuterol use is defined as the mean number of inhalations per day from day 1 to day 7. If no inhalations were taken during study day 1 through study day 7, the ‘baseline inhalation’ is the first available inhalation after study day 7. For analyses relative to baseline albuterol use, patients who had a CE-COPD during study day 1 through study day 7 will be excluded.

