4.5. Study Day and Study Week

Study days will be numbered relative to the earliest date an ABS eMDPI device was dispensed (ie, ... -2, -1, 1, 2, ...). Day 1 is defined as the earliest date an ABS eMDPI device was dispensed and Day -1 is the day before the first ABS eMDPI device was dispensed.

Week I is defined as study day $(j + 1)$ to study day $(j + 7)$, inclusive where $I = 1$ to 12 and $j = 0, 7, 14, 21, 28, 35, 42, 49, 56, 63, 70, 77, 84$, respectively.

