7.3. Accelerometry: Total Daily Steps

7.3.1. Total Daily Steps Definition

Study Day X and Week Y TDS are defined as follows:

Study Day X TDS: The TDS for study day X are the TDS recorded by accelerometry on study day X . If TDS are missing on Study Day X , then the average TDS of the 7 days preceding study day X is computed and assigned to Study Day X .

Week Y TDS: The TDS for Week Y are computed using the set of TDS taken by the patient during a given week on study. The average will be calculated as the sum of the daily TDS divided by the number of days with nonmissing TDS.

The TDS are computed for those patients in the ankle accelerometry analysis set.

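### The albuterol-use and daily-step baselines count the partly observed dispensing day as a full day, so both are expected to be too low: about 7% if half of that day is captured, at most 14% with all seven days present.

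*SAP*

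**What the plan says.** SAP 4.5 fixes the calendar: "Day 1 is defined as the earliest date an ABS eMDPI device was dispensed". Protocol Appendix B places that dispensing at "Baseline Visit (Visit 2, Day 1". According to the schedule footnote in SAP 2.1, accelerometers "will be dispensed at visit 2, and SDI and TDS data will be collected continuously from visit 2 through visit 5".

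For albuterol, SAP 4.2.1 (repeated in 7.1.1) states: "Baseline albuterol use is defined as the mean number of inhalations per day from day 1 to day 7". For steps, SAP 4.2.4 uses an average "computed using the daily steps recorded during the first 7 days of study participation (study day 1 through study day 7" and adds: "The average will be calculated as the sum of the daily TDS divided by the number of days with nonmissing TDS". Neither section drops Day 1, adjusts it for hours observed, or sets a minimum wear time. A fallback to the first value after day 7 applies only when the whole window is empty; for steps the condition is "If no step data are available for study day 1 through study day 7".

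For weekly steps, SAP 7.3.1 says: "The TDS for Week Y are computed using the set of TDS taken by the patient during a given week on study", again averaged over nonmissing days. Week 1 is study days 1 to 7.

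**The concern.** Inhalations and steps taken on Day 1 before visit 2 cannot be recorded. That day still enters each average with the same weight as a fully observed day, because a partial count is a nonmissing count. The expected error goes one way: the baseline is low.

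The step baseline feeds the change-from-baseline summaries in SAP 7.3.2. The albuterol baseline reaches further:

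- the +20%, +2 and +4 inhalation thresholds (7.1.2.4);
- the summaries of days and weeks at or below average baseline use (7.1.2.1);
- the rule that a later exacerbation is distinct only if a day of baseline-level use came in between (7.1.2.2, 7.2.2.1, 7.3.2.1);
- the first day 20% above baseline use, at which flow, step and sleep values are also summarised (7.2.2.1, 7.3.2.1, 7.4.2.1).

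A low baseline makes an increase easier to reach, and a day of baseline-level use harder to reach, with no clinical change.

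**Working it through.** The plan states no figure for this point, so there is none to reproduce.

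**Inputs.** The window is days 1 to 7 (SAP 4.2.1, 4.2.4). f, the share of a normal day's use or steps captured on Day 1, is an assumption because the hour of visit 2 is not given; it is shown from 0 to 0.75. Two illustrative levels are used: 5804 steps/day from the cohort cited in Protocol 3.3, and 4 inhalations/day from the SAP 7.1.1 example (28 in 7 days).

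**Formulas, for a patient whose true level is stable.**

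- Baseline ratio r = (6+f)/7; shortfall = 1 − r = (1−f)/7.
- Apparent rise when nothing has changed = 1/r − 1.
- True rise at which the nominal +20% line is met = 1.2r − 1.
- Step offset = 5804 × (1−f)/7; inhalation offset = 4 × (1−f)/7.

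| f | r | Shortfall | Apparent rise | True rise meeting +20% | Steps/day | Inhalations/day |
|---|---|---|---|---|---|---|
| 0 (limit) | 0.857 | 14.3% | 16.7% | 2.9% | 829 | 0.57 |
| 0.25 | 0.893 | 10.7% | 12.0% | 7.1% | 622 | 0.43 |
| 0.5 | 0.929 | 7.1% | 7.7% | 11.4% | 415 | 0.29 |
| 0.75 | 0.964 | 3.6% | 3.7% | 15.7% | 207 | 0.14 |

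**Fewer step days.** The step average divides by nonmissing days, so with k such days including Day 1 the shortfall is (1−f)/k. At f=0.5 this is 0.5/3 = 16.7% with three days, and 50% if Day 1 is the only day.

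**Week 1 steps.** The Week 1 mean and the baseline are the same average over the same days, so the change is exactly 0 for every f. The offset appears from Week 2 onward.

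**Whole-number counts.** Take exactly 4 inhalations every day, with 2 captured on Day 1. The baseline is 26/7 = 3.71.

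- The +20% line moves from 4.80 to 4.46, so 5 inhalations are needed either way.
- The +2 line moves from 6 to 5.71 and the +4 line from 8 to 7.71, so 6 and 8 are still needed.
- The at-or-below-baseline pattern does change: 4 exceeds 3.71, so every later day counts as above baseline.

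**With day-to-day variation.** A simulation used Poisson counts at 4/day, f=0.5, 100,000 stable patients and days 8 to 84.

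| Quantity | Baseline days 1–7 (SAP) | Baseline days 2–7 |
|---|---|---|
| Mean baseline | 3.72 | 4.00 |
| Days at or above +20% | 40.0% | 35.7% |
| Days at or above +2 | 21.2% | 18.3% |
| Days at or above +4 | 5.4% | 4.5% |
| Days at or below baseline | 49% | 54% |

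Had all of Day 1 been observed (f=1), the seven-day baseline would flag 34.5% of days at +20%. The gap from 34.5% to 35.7% is the price of one day fewer in the average.

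**The case against.** The strongest reply is that the affected outputs are unadjusted descriptive summaries in an exploratory study, and that the main comparisons do not use this baseline. That stands. The t-test in SAP 7.1.2.3 sets days 1–7 against days 8–14 before the symptom peak. The comparison in 7.5.2.1 uses the two weeks before symptom onset. The landmark analysis in 7.5.2.2 uses fixed counts. The partial Day 1 can enter the first two directly only when the event falls by about Study Day 15 (15 − 14 = 1).

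A reader might infer that every change from baseline is inflated. The documents do not support that. Week 1 step change is 0, and fallback baselines and patients with no Day 1 step value are unaffected. Albuterol has thresholds and patterns rather than a tabulated change. The flow baseline is the inhalation with the highest MIF, and the sleep baselines are mainly nighttime values, so this arithmetic does not carry over to them.

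A reader might also infer that a fall in steps before an exacerbation would be hidden. It would not: SAP 7.3.2.1 reports actual steps as well as changes, and a patient's offset is constant, so it cancels between 21 days and 1 day before the peak. Nor should 415 steps be read against the risk per 1000 steps in Protocol 3.3, which is a between-patient association in another cohort.

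Finally, ordinary daily variation causes most threshold crossings, as the simulation shows. This limits the size of the problem. It does not remove an error that is expected to run in one direction and is avoidable.

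**Conclusion.** The point holds for the albuterol-use and step baselines. Each is expected to be low by (1−f)/7 with all seven days present: about 7% at f=0.5, 3.6% at 0.75, 10.7% at 0.25, never above 14.3%, and more for steps when days are missing. Step changes after Week 1 are shifted upward. The albuterol threshold summaries, the at-or-below-baseline pattern and the distinct-exacerbation rule are distorted.

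The direction follows from the SAP's own definitions; the size rests on f, which is assumed. Two further points are unstated and could alter the albuterol shortfall: whether a training inhalation at visit 2 is recorded on the dispensed device, and whether the denominator in SAP 4.2.1 is seven days or days with use. The bias is an expectation over patients and need not hold for each one. The change should be made, but it does not put the hypothesis test at risk.

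**What to change.** Compute both baselines as the mean over study days 2 to 7, and state the albuterol denominator. Omit Day 1 from the Week 1 step mean, so that Week 1 and baseline remain the same quantity. Keep the exclusion of patients with an exacerbation on days 1 to 7, and keep the fallback to the first value after day 7, worded so that a patient with data on Day 1 only goes to the fallback.

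Two alternatives are less suitable. A window of days 2 to 8 would cross into Week 2 and no longer match the exclusion and fallback rules. A blanket removal of device-return days is not supported: Protocol Appendix B has inhalers collected, and replaced if needed, at exacerbation visits, so it could delete observed days close to the events of interest.

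The cost is SAP wording only, with no new data. The downside is one fewer day in the baseline average and therefore slightly more noise. At low use this can outweigh the gain on the +20% threshold: in the same simulation at 2 inhalations/day and f=0.75, flagged days go from 38.2% to 39.3%. The expected bias in the baseline itself becomes zero for any f.

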4.2.5. Sleep Parameters

There are 8 measures of sleep disruption: (i) nighttime average total time in bed, (ii) nighttime average total sleep time, (iii) nighttime average sleep latency time, (iv) nighttime average wakening after sleep onset, (v) total time awake at night, (vi) daytime average minutes asleep, (vii) longest daytime sleep episode and (viii) longest nighttime wake episode. The first 7 sleep parameters are provided via Philips accelerometry and longest nighttime wake episode is derived from the accelerometry data as follows:

The sleep interval data provided via Philips accelerometry includes the activity state ("sleep"/"awake") every 30 seconds during the sleep interval. The number of successive 30 second "awake" states occurring between "sleep" states within the sleep interval is summed to determine the duration of a given "awake" state. The longest nighttime wake episode is the summated "awake" state with the longest duration during the sleep interval.

The baseline value of a given sleep parameter (eg, nighttime average total time in bed) is the average sleep parameter (eg, nighttime average total time in bed), computed using the sleep parameter (eg, nighttime average total time in bed) values captured by accelerometry during study day 1 through day 7. The average will be calculated as the sum of the average sleep parameter divided by the number of days with nonmissing values of the average sleep parameter. If no sleep parameter data are available for study day 1 through study day 7, the 'baseline value of a given sleep parameter' is the first available valid sleep parameter value after study day 7.

Baseline sleep parameters are computed for those patients in the wrist accelerometry analysis set.

4.3. Time on Study

Time on study is the number of days from date of informed consent to date of completion or last contact date plus 1.

4.4. eMDPI Time on Study

The eMDPI time on study is the number of days (D_{emdpi}) from the last device return date to the date the first ABS eMDPI device was dispensed. For instances where the last device return date is missing the patient's last date of contact or study completion, date will be used, whichever comes first.

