7.1.2. Analysis Methods for Albuterol Use

7.1.2.1. Pattern of Baseline Daily and Weekly Albuterol Use

A patient's pattern of baseline albuterol use is exhibited if, on any given day, during a given week, they do not take more than their average number of inhalations computed from day 1 to day 7.

Summary statistics including 95% CIs intervals of the proportion of patients exhibiting their individual weekly baseline albuterol use during each week of the 12 week study (Week 1, Week 2,..., Week 12) will be presented overall and by CE-COPD status and by CE-COPD severity (Yes: severe, moderate; No).

Summary statistics including 95% CIs intervals of the proportion of eMDPI time on study days when a patient did not take more than the average number of inhalations computed from day 1 to day 7 (number of days a given patient had no more than average baseline albuterol use) / total number of eMDPI study days for a given patient) will be summarized overall and by CE-COPD status and by CE-COPD severity (Yes: severe, moderate; No).

Week 1 and Week 2 and the first 14 day patient albuterol use patterns, "WK1:I#iD#dMTN#n," "WK2:I#iD#dMTN#n" and "D14:I#iD#dMTN#n" designation, will be summarized descriptively (counts and percent) overall and by CE-COPD status and by CE-COPD severity (Yes: severe, moderate; No).

7.1.2.2. Total Number of Inhalations in the Days Preceding the Peak of a CE-COPD

For patients who experienced a CE-COPD, summary descriptive statistics of the total number of inhalations taken in 1 day (eg, the 24-hour period on the day prior to the date of the CE-COPD symptom peak) and at 3, 5, 7, 10, 14, and 21 days preceding the date of the CE-COPD symptom peak, will be presented overall and by moderate CE-COPDs and severe CE-COPDs.

In this analysis, among patients experiencing more than 1 CE-COPD, the subsequent CE-COPDs can be considered a separate CE-COPD, distinct from the first (preceding) CE-COPD, provided the patient exhibited at least 1 day of baseline albuterol use after the first (preceding) CE-COPD's end date, as captured on the adverse event page, and prior to the subsequent CE-COPD's start date, as captured on the adverse event page. For patients who experience multiple CE-COPDs, all distinct CE-COPDs will be considered in this descriptive analysis. Descriptive summaries of the number of inhalations on the days prior to a CE-COPD will only be reported if the event does not overlap with a preceding CE-COPD. For example, if the date of symptom

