Clinical Exacerbation of COPD Status: Clinical exacerbation of COPD status is an indicator of whether or not a patient experienced a CE-COPD during study follow-up (Yes, No).

Clinical Exacerbation of COPD Rate: The percentage of patients who experience at least 1 moderate or severe CE-COPD at the end of study follow-up.

Recurrent Clinical Exacerbation of COPD Rate: The percentage of patients who experience more than 1 moderate or severe CE-COPD at the end of study follow-up.

Time to Clinical Exacerbation of COPD: Time, in days, from Study Day 1 to the Date of Symptom Peak plus 1.

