10.2. Duration of Exposure to ABS eMDPI

Duration of exposure to ABS eMDPI (days and weeks) for the individual patient is the number of days the patient took at least 1 inhalation from the ABS eMDPI. Patients receive the ABS eMDPI devices at Baseline and subsequently by courier on Day 21. Duration of exposure is determined from all eMDPIs used by a patient and it is the total number of unique dates recorded by the eMDPIs from the dispense date and return date of a given device, inclusive. Note, if a patient uses more than 1 eMDPI device on a given day, it is still only 1 day of exposure for that given day. The patient's last date of contact or study completion date will be used as the device return date if the device return date is missing.

Duration of exposure (days and weeks) will be summarized using descriptive statistics overall, and by CE-COPD status and by CE-COPD severity.

Exposure to IMP, expressed in mcg units, will also be summarized using descriptive statistics. Average daily exposure, average weekly exposure, and the maximum exposure in a single day will be summarized overall, and by CE-COPD status and CE-COPD severity. One inhalation recorded by the ABS eMDPI is equivalent to 90 mcg.

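### SAP 4.4 leaves eMDPI time on study one day short of the SAP's own inclusive convention, which slightly inflates any proportion of days that uses it as denominator

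*SAP*

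**What the plan says.** SAP 4.4 defines eMDPI time on study (D) as the number of days "from the last device return date to the date the first ABS eMDPI device was dispensed". The two dates stand in reverse order, and nothing is added to the difference.

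Four other places in the SAP count inclusively:

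- 4.3, directly above: "Time on study is the number of days from date of informed consent to date of completion or last contact date plus 1".
- 7.5.1, for time to exacerbation: "Time, in days, from Study Day 1 to the Date of Symptom Peak plus 1".
- 4.5, for study-day numbering: "Day 1 is defined as the earliest date an ABS eMDPI device was dispensed". There is no Day 0.
- 10.2, for exposure: "the total number of unique dates recorded by the eMDPIs from the dispense date and return date of a given device, inclusive".

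The quantity is used in three places. SAP 5.10 tabulates it in days and in weeks (days divided by 7). SAP 7.1.2.1 summarises, per patient, the "number of days a given patient had no more than average baseline albuterol use" divided by the "total number of eMDPI study days for a given patient". SAP 7.1.2.4 gives a ratio with the same denominator for patients without an exacerbation. In both of the last two, the sentence introducing the ratio repeats the term that 4.4 defines. SAP Section 20, which lists departures from the protocol, gives no other denominator.

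**The concern.** 4.3 and 4.4 are adjacent and phrased alike, and only the first adds a day. A programmer following the text would add 1 in 4.3 and not in 4.4.

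Study days are numbered from the dispensing date, and baseline starts there too: "Baseline albuterol use is defined as the mean number of inhalations per day from day 1 to day 7". A device returned on Day k therefore gives k countable study days, while 4.4 gives k − 1. If the numerator counts study days and the denominator is D, the two cover different windows. The proportions come out slightly too high, and a patient who qualifies on every day would be reported above 100%.

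The tables could also disagree with each other. Someone who inhales every day and returns the device on Day 84 would show 84 days of exposure under 10.2 against 83 days of eMDPI time on study under 5.10.

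**Working it through.** The plan gives no figure of its own to reproduce, so the check is date arithmetic.

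**Inputs.** D = last return date − first dispensing date (SAP 4.4 read as a plain difference). Day 1 = dispensing date (SAP 4.5). The final visit falls on Day 84 ± 14, that is Day 70 to Day 98 (protocol Table 1, SAP Table 1).

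**Formula.** A return on study day k gives D = k − 1 and D + 1 = k countable days. With n qualifying days, the ratio as written is n/D, against n/(D+1) on an inclusive count. The inflation factor is (D+1)/D for any n > 0. It is also the largest value the ratio can take.

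| Return on study day | D under 4.4 | Countable days | (D+1)/D |
|---|---|---|---|
| 7 | 6 | 7 | 7/6 = 116.7% |
| 14 | 13 | 14 | 14/13 = 107.7% |
| 28 | 27 | 28 | 28/27 = 103.7% |
| 70 | 69 | 70 | 70/69 = 101.4% |
| 84 | 83 | 84 | 84/83 = 101.2% |
| 98 | 97 | 98 | 98/97 = 101.0% |

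For SAP 5.10, a Day 84 return gives 83/7 = 11.86 weeks as written and 84/7 = 12.00 weeks inclusively.

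**Who can exceed 100%.** The ratio passes 100% only if n = D + 1, that is, if every countable day qualifies.

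- *7.1.2.1 (days at or below the patient's own baseline mean).* No day can lie above the Day 1 to 7 mean, so use on Days 1 to 7 must be constant and later use no higher. Constant users meet this. Never-users meet it if their baseline is taken as 0, which 4.2.1 does not state.
- *7.1.2.4, the ratio for days above 4 inhalations.* This needs more than 4 inhalations on every day.
- *7.1.2.4, the listed thresholds relative to baseline (20%, 2 and 4 inhalations).* These cannot reach D + 1 when baseline is the Day 1 to 7 mean, because at least one of those days does not exceed its own mean.

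**How often.** Simulation of 20,000 patients per scenario, all returning on Day 84. The use patterns are assumptions, because the documents give no distribution of daily use.

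| Assumed daily use | 7.1.2.1 above 100% | Same, baseline set to 1 if no use on Days 1 to 7 but some later | 7.1.2.4 ratio for more than 4 inhalations above 100% |
|---|---|---|---|
| none | 100% | 100% | 0 |
| Poisson 0.005 | 65% | 96% | 0 |
| Poisson 0.02 | 19% | 86% | 0 |
| Poisson 0.1 | 0.02% | 35% | 0 |
| Poisson 0.5, 2 or 5 | 0 | 0 | 0 |
| Poisson 8 | 0 | 0 | 0.02% |
| Poisson 12 | 0 | 0 | 53% |
| constant 5 | 100% | 100% | 100% |

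The thresholds relative to baseline never exceeded 100% in any scenario.

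**After the fix.** With D + 1 as denominator the maximum is exactly 100% for every return day.

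**The case against.** The strongest reply is that the denominator is inferred. Neither 7.1.2.1 nor 7.1.2.4 cites 4.4 or its symbol, and the printed formulas speak of eMDPI study days. SAP 7.1.2.2 uses that phrase in the singular for the numbered study day on a plot axis. Counting numbered days from Day 1 gives the inclusive total, and the mismatch disappears. Nor does the SAP state the date window of the numerators. The inclusive rule in 10.2 governs days with at least one inhalation, which is a different count. It can also be said that 4.4 is loose prose rather than a subtraction formula, and that elapsed days are a defensible duration when the dispensing and return dates are both partial days.

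Most of this stands as a limit on the claim. The inflation of the proportions is conditional on a reading that the shared term favours but no cross-reference fixes. What does not fall away is that 4.4 departs from the convention in 4.3, 4.5, 7.5.1 and 10.2, and that 5.10 reports the 4.4 quantity directly.

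A reader might infer more: that the proportions are demonstrably overstated, or that values above 100% will be common in both sections. The documents do not support that. The link to D is by wording only, and values above 100% need every day to qualify. In the simulation none arose in 7.1.2.1 under Poisson use of 0.5 inhalations a day or more. A return on the dispensing date would give a zero denominator, but nothing in the documents suggests how often that would happen, if ever.

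**Conclusion.** There is a small off-by-one in a stated rule. Read as a plain difference, SAP 4.4 is one day short for every patient by the SAP's own convention, and this shows in 5.10 whichever denominator is used elsewhere.

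Two assumptions carry the rest: that 7.1.2.1 and 7.1.2.4 divide by D, and that their numerators count study days from Day 1 through the return date. Under both, non-zero proportions are inflated by between 1.0% and 1.4% in relative terms for returns in the final-visit window, and by more for early leavers. Values above 100% are confined to constant users, some very low users and possibly never-users in 7.1.2.1, and to patients above 4 inhalations on every day in 7.1.2.4.

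The matter is minor. These are descriptive summaries in an exploratory study. The t-test in 7.1.2.3, the exacerbation outcome and the sample size do not depend on it.

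**What to change.** In SAP 4.4, define eMDPI time on study as the last device return date minus the first dispensing date plus 1, with the same plus 1 when a substitute date replaces a missing return date. In 7.1.2.1 and 7.1.2.4, state that numerator and denominator use this same set of days. That brings 4.4 into line with 4.3, 4.5, 7.5.1 and 10.2, caps the proportions at 100% and removes the zero denominator for a same-day return. The cost is one term in 4.4, one sentence in each of the other two sections and the matching line of code. No data collection or other analysis changes.
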